9.3 Populations for Analyses

There are 7 populations defined for this study ([Table 11](#)).

Table 11 Populations for Analyses

Population	Description
ITT	All randomized participants will be included in the ITT Population. Participants will be analyzed according to their randomized intervention group. Participants randomized to the CCI mg group that switch dose to CCI mg during the trial will be analyzed according to the CCI mg group.
As-treated	Randomized participants who receive any study intervention will be included in the As-treated Population. Participants will be analyzed according to the actual intervention they receive, regardless of their randomized intervention group. Participants randomized to the CCI mg group that receive at least one CCI mg dose during the study will be analyzed according to the CCI mg group. Participants that only receive CCI mg will be analyzed as a separate CCI mg group.
CTA Analysis	Participants within the ITT population who have interpretable CTA scans at baseline and at least one post-baseline time point will be included in the CTA Analysis Population.
Per-protocol CTA analysis	Participants in the CTA Analysis Population who receive at least 3 doses of study intervention will be included in the Per-protocol CTA Analysis Population. Participants will be analyzed according to the actual intervention they receive.
Echocardiogram Analysis	Participants within the ITT population who have interpretable echocardiograms in the baseline and follow-up periods will be included in the Echocardiogram Analysis Population.
PK	All participants who receive ≥ 1 dose of MEDI6570 per protocol and have ≥ 1 post-dose, evaluable, MEDI6570 serum concentration determination will be included in the PK analysis set.
Immunogenicity	Participants included in the As-treated Population who have ≥ 1 immunogenicity sample will be included in the Immunogenicity Population.

CTA, computed tomography angiography; ITT, Intent-to-treat; PK, pharmacokinetic.

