PK population	
All subjects who received ≥ 1 dose of MEDI6570 and have ≥ 1 one post-dose evaluable MEDI6570 serum concentration will be included in the PK population.
 
Subjects will be analysed according to the actual treatment they received. Subjects who received both CCI doses during the study will be analysed as a separate CCI group.

Immunogenicity population	
Subjects included in the As-treated Population who have ≥ 1 immunogenicity sample will be included in the Immunogenicity Population.
 
Subjects will be analysed according to the actual treatment they received.

* All subjects randomized in initial CSP accepted CSP amendment 1 and took at least one dose under CSP amendment 1. This means that any subject initially randomized in **CCI** have taken at least one dose of **CCI**

**An interpretable CTA scan is defined as having 1 or more matching evaluable segment at baseline and at Day 253 or at Day 122. LOCF (Last Observation Carried Forward) method not applied. The baseline scan must have quantifiable plaque present after segment matching to be interpretable. Programming specifics on matching evaluable segments are detailed in a separate CTA imaging guidance document (Version 4.0).

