4.2.9.1 Immunogenicity analysis

The endpoints to evaluate immunogenicity of MEDI6570 are ADA incidence and Titre. ADA and Titre are described in section 3.3.3.1. Baseline and post-baseline definitions are detailed in section 3.1.2. Tables and listings will be based on the Immunogenicity population and presented for each treatment group and overall (total will not include placebo subjects).

ADA will be summarised in IDMC reports (if data available prior to the meeting) and at final analysis using the following categories:

- ADA negative at all assessments, including baseline and post-baseline (ADA negative)
- ADA positive at baseline and/or post-baseline (ADA prevalence)
- TE-ADA positive (ADA incidence)
- Treatment-induced ADA positive
- Treatment-boosted ADA positive
- TE-ADA negative
- Both baseline and post-baseline positive
- Only baseline positive
- ADA persistently positive
- ADA transiently positive
- TE-ADA positive with maximum titre > median of maximum titres.

ADA negative is defined as having ADA negative at all assessment, including baseline and post-baseline. TE-ADA positive is defined as the sum of treatment-induced ADA positive (ADA negative at baseline and post-baseline ADA positive) and treatment-boosted ADA positive (ADA positive at baseline and boosted the pre-existing titre during the study period).

TE-ADA negative is defined as ADA positive but not fulfilling the definition of TE-ADA positive. ADA incidence is the proportion of TE-ADA positive subjects in a population.

ADA persistently positive is defined as ADA negative at baseline and ADA positive at ≥ 2 post-baseline assessments (with ≥ 16 weeks between first and last positive) or ADA positive at last post-baseline assessment. ADA transiently positive is defined as ADA negative at baseline, having at least one post-baseline ADA positive assessment and not fulfilling the conditions of ADA persistently positive.

The median of maximum titres is calculated based on the maximum titre for each ADA positive subject within each treatment group (including both baseline and post-baseline measurements).

ADA will be also reported in a listing in IDMC reports (if data available prior to the meeting) and at final analysis.

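### ADA incidence should be computed among participants with a baseline and a post-baseline ADA result; the current denominator can only lower it, probably by little

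*SAP*

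**What the plan says.** **Population.** SAP 2.1 (Table 2) says that As-treated subjects with at least one "immunogenicity sample will be included in the Immunogenicity Population". Protocol 9.3 (Table 11) has the same rule: "Participants included in the As-treated Population who have ≥ 1 immunogenicity sample will be included in the Immunogenicity Population". Neither asks for a baseline sample or for a post-baseline sample.

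**Use.** SAP 4.2.9.1: "Tables and listings will be based on the Immunogenicity population and presented for each treatment group and overall".

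**Measure.** The same section says that "ADA incidence is the proportion of TE-ADA positive subjects in a population". It does not name the population and defines no ADA-evaluable subset.

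**Classes.** There are two routes to TE-ADA positive:
- induced: "TE-ADA positive is defined as the sum of treatment-induced ADA positive (ADA negative at baseline and post-baseline ADA positive";
- boosted: "treatment-boosted ADA positive (ADA positive at baseline and boosted the pre-existing titre during the study period".

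The other class is a residual: "TE-ADA negative is defined as ADA positive but not fulfilling the definition of TE-ADA positive". Persistent and transient positivity both start from a negative baseline.

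**Missing values.** Under SAP 3.1.2 a baseline with no pre-dose value stays missing, and SAP 3.1.1 provides no imputation that would apply to ADA.

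**Schedule.** Under Amendment 2 (Protocol 1.3, Table 4) the immunogenicity samples in the intervention period fall on Days 1, 29, 57, 113 and 169, with the sample taken before the dose on dosing days. The amendment removed the Day 10 sample.

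**The concern.** Treatment emergence is a statement about change from baseline, so it can be judged only in someone with both ends of the comparison. The plan divides by a population that does not require both. A participant who cannot be judged then counts the same in the denominator as one who was followed throughout and stayed negative.

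The residual definition raises a second problem: a participant whose emergence cannot be known is placed in a class named negative. The classification matters beyond the incidence line. SAP 4.2.10.7 plans adverse-event tables by ADA category on the same population, and SAP 4.2.9.2 plans concentration plots by ADA category. Mixing unknown with negative blurs those comparisons.

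The rule is also out of step with the rest of SAP 2.1. The CTA and echocardiogram populations need a baseline and a later image, and the PK population needs an evaluable post-dose concentration. ADA incidence depends on a baseline comparison, yet its population has no such condition.

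**Working it through.** The documents state no ADA rate, count or power figure, so there is nothing to reproduce. The check is one of logic, followed by an identity.

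**Step 1: who can be positive.** The induced route needs a negative baseline and a positive later result. The boosted route needs a positive baseline and a raised later titre. So every TE-ADA positive participant has a pair.

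**Step 2: the identity.** Let N_imm be the Immunogenicity population, N_eval the participants in it with a baseline and at least one post-baseline ADA result, and x the number who are TE-ADA positive. By step 1, all x lie within N_eval. With m = 1 − N_eval/N_imm,

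x/N_imm = (x/N_eval) × (N_eval/N_imm) = (x/N_eval) × (1 − m).

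The reported figure can never exceed the figure among paired participants. It is lower whenever m > 0 and x > 0, and the relative shortfall equals m.

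**Step 3: size.** Both inputs are assumptions. Reported incidence:

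| Incidence among paired participants | m = 0 | m = 2% | m = 5% | m = 10% |
|---|---|---|---|---|
| 5% | 5.0% | 4.9% | 4.75% | 4.5% |
| 10% | 10.0% | 9.8% | 9.5% | 9.0% |
| 20% | 20.0% | 19.6% | 19.0% | 18.0% |
| 30% | 30.0% | 29.4% | 28.5% | 27.0% |

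For m from 2% to 10% the shortfall runs from 0.1 point (5% × 2%) to 3.0 points (30% × 10%).

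**Step 4: counts, for illustration only.** Take an arm of 123, the planned size of each continuing active group (Protocol 4.1). Suppose 4 have no baseline, 8 have no post-baseline result and 11 are TE-ADA positive. Then N_eval = 123 − 4 − 8 = 111 (this has no link to the planned number of CTA-evaluable participants).
- Current denominator: 11/123 = 8.9%.
- Paired denominator: 11/111 = 9.9%.
- Sensitivity count, if 2 of the 4 with a missing baseline are positive later and are counted as emergent, over all with a post-baseline result: 13/(123 − 8) = 13/115 = 11.3%.

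**Step 5: the residual class.** A participant with no baseline and a positive later result meets the prevalence category, which accepts a positive result at either time. The same participant meets neither route to TE-ADA positive. The residual definition then gives the label TE-ADA negative.

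**The case against.** The strongest reply is that this is a gap in wording with little practical effect, and much of that stands.

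- **Missing baselines should be rare.** The Day 1 sample is planned before dosing, Protocol 6.3.1 places randomization after the Day 1 blood collection, and SAP 3.1.2 treats an untimed Day 1 measurement as pre-dose where the protocol plans it so. What remains is deviations and lost or failed samples.
- **The denominator is not spelled out.** SAP 4.2.9.1 refers only to a population, and there is no explicit rule for a missing ADA baseline. The Immunogenicity population is the natural reading because the tables rest on it, but it remains a reading.
- **Nothing disappears from the report.** A later positive with a missing baseline still counts in prevalence and appears in the listing of ADA-positive subjects.
- **No test is affected.** ADA incidence is descriptive. In an arm of 123, a shortfall of 0.5 point is 0.6 of a participant.

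A reader might infer two stronger points that the documents do not support.

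The first is that everyone who leaves before Day 29 has only a baseline sample. Participants enrolled before Amendment 2 had a Day 10 sample scheduled. Protocol 8.5.2 allows extra samples, and SAP 4.2.9.1 includes unscheduled measurements in all ADA analyses except the by-visit summary. Participants who only stop treatment remain in the study for assessments (Protocol 7.1). The group is therefore those who leave the study before the first post-baseline sample and have no unscheduled one.

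The second is that each positive with a missing baseline costs a further 1/123, or 0.8 point. Such participants are already inside m, so this would count them twice. A paired denominator also removes them from numerator and denominator alike. With no baseline, the later positive may have been present before treatment, so it cannot be called lost emergent ADA.

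None of this removes the mechanism: if any pair is incomplete and any participant is TE-ADA positive, the planned ratio is too low.

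**Conclusion.** The point holds as a low-priority correction. On the natural reading of SAP 4.2.9.1, reported ADA incidence is the incidence among paired participants multiplied by (1 − m). The direction is certain whenever m > 0 and at least one participant is TE-ADA positive; the size is not known. At an assumed 10% incidence the figure becomes 9.8% (m = 2%) or 9.5% (m = 5%), and with complete pairs there is no bias. Separately, the residual wording classes the rare positive with a missing baseline as TE-ADA negative when its status is unknown. No hypothesis test, significance level or power figure is touched.

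**What to change.** In SAP 4.2.9.1:

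1. State that ADA incidence and the TE-ADA positive, TE-ADA negative, induced, boosted, persistent and transient categories are computed among participants with a baseline and at least one post-baseline ADA result.
2. Show post-baseline positives with a missing baseline as a separate category rather than as TE-ADA negative, and add a sensitivity count that treats them as treatment-emergent.
3. Keep the present Immunogenicity population for prevalence.

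Protocol 9.4.2.2 assigns the immunogenicity analyses to the Immunogenicity population, so the narrower denominator should be recorded in SAP section 6.

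The cost is a few SAP sentences and no new data. The downside is a slightly smaller denominator for incidence, so each table should show both denominators.

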2.2 Violations and deviations

The protocol deviation management plan (PDMP) categorizes the important and non-important protocol deviations and outlines how the deviations are handled.

3 BASELINE, PRIMARY, SECONDARY, EXPLORATORY AND SAFETY VARIABLES

3.1 General principles

3.1.1 Handling of missing data

Except for the below and unless otherwise specified, missing data will not be imputed.

3.1.1.1 Imputation of time of first dose of IP

Completely missing time where only hour is missing will be imputed to 00:00. If the time (hours/minutes: HH:MM) of the first dose of IP is completely missing or the hour HH is missing, imputation will be 00:00. If only the minutes are missing imputation will be HH:00. .

3.1.1.2 Imputation of adverse event / concomitant medication start date

Missing start dates (where in eCRF UN, UNK and 0000 indicate unknown or missing Day, Month and Year respectively for partial missing dates, while completely missing dates would be left empty):

- Completely missing dates will not be imputed.
- If the day is missing and the month and year are different from the month and year of the first dose of study treatment, assume 01-MMM-YYYY. If the month and year are the same as the first dose of IP month and year and the end date (after any imputation) is on or after (including still on-going/ missing at the end of the study) the first dose of IP, then assume the date of the first dose of IP. If the month and year are the same as the first dose of IP month and year and the end date (after any imputation) is prior to the first dose of IP, then assume the end date for the start date.
- If the month is missing and the year is different from the year of first dose of IP, assume 01-JAN-YYYY of the collected year. If the year is the same as the first dose of IP and the end date (after any imputation) is on or after (including still on-going/ missing at the end of the study) the first dose of IP, then assume the date of the first dose of IP. If the year is

the same as the first dose of IP and the end date (after any imputation) is prior to the first dose of IP, then assume the end date for the start date.

After applying these rules, if the imputed AE start date is after a complete AE end date (or date of death or date of end of study), the imputed start date will be the same as the complete AE end date (or date of death or date of end of study); if the end date is missing and the imputed AE start date is after the end of study date then assume the same date as the study end date.

CCI

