3.5 Concomitant medications

The most up to date version of WHO Drug Dictionary (WHO-DD) is used to classify medications by World Health Organization (WHO) Anatomical Therapeutic Chemical (ATC) classification of ingredients.

The imputation method described in section [3.1.1.2](#) and [3.1.1.3](#) is used in case of medication start date or stop date partially missing. Completely missing concomitant medication start dates and stop dates are not imputed.

After the end date imputation, the medications will be classified as either prior or concomitant (but not both) according to its stop date. Concomitant medication is defined as any medication with a stop date on or after the first dose of study drug, or any medication taken prior to study

drug and that is ongoing. Medications with completely missing stop date are classified as concomitant.

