4.2.4 Concomitant medications

Concomitant medications are defined in section [3.5](#). The number and percentage of subjects with at least one concomitant medication and the number and percentage of subjects by ATC level 4 and product name will be provided using the ITT population at final analysis only.

Additionally, the number and percentage of subjects with at least one cardiac medication will be presented using the ITT population at final analysis only. Cardiac medications include the following ATC level 2 classifications: antithrombotic agents, agents acting on the renin-angiotensin system, beta blocking agents, drugs used in diabetes, and lipid modifying agents. Only medications started prior to randomization or ongoing at the end of study will be summarized.

Cardiac concomitant medication started prior to randomization is defined as any medication with a start date prior to randomization date.

Cardiac concomitant medication ongoing at end of study is defined as any medication with a start date prior to or on the date of end of study or ongoing or no end date.

Concomitant medications will be listed for the ITT population at final analysis.

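### The start-date rule shared by AEs and medications moves some partial dates to first dose, so cardiac drugs truly begun earlier in that year or month drop out of the pre-randomization category

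*SAP*

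**What the plan says.** The rule in SAP 3.1.1.2 is headed "Imputation of adverse event / concomitant medication start date", and SAP 3.5 confirms that it "is used in case of medication start date or stop date partially missing". For a drug that is ongoing, or that stopped on or after first dose, it has four branches:

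- **Day missing, other month or year.** Where these "are different from the month and year of the first dose of study treatment, assume 01-MMM-YYYY".
- **Day missing, month and year of first dose.** The start becomes the first-dose date.
- **Month missing, other year.** "If the month is missing and the year is different from the year of first dose of IP, assume 01-JAN-YYYY".
- **Month missing, year of first dose.** "If the year is the same as the first dose of IP and the end date (after any imputation) is on or after" first dose, "then assume the date of the first dose of IP".

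SAP 4.2.4 summarizes subjects with cardiac medication (antithrombotic, renin-angiotensin, beta-blocker, diabetes and lipid-modifying classes) in two categories. The first is defined thus: "Cardiac concomitant medication started prior to randomization is defined as any medication with a start date prior to randomization date". The second is medication ongoing at the end of study.

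Protocol 6.3.1 places randomization on Day 1 (Visit 3), and Protocol 4.1 places the first dose on the same day, after randomization.

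**The concern.** For adverse events the rule is conservative: an event of uncertain onset is treated as emerging on treatment. For medications that purpose is absent. Under SAP 3.5 "the medications will be classified as either prior or concomitant (but not both) according to its stop date", so moving a start date to Day 1 changes nothing there. What it does change is the one visible output that depends on medication start dates, the pre-randomization category in SAP 4.2.4.

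That category matters for reading this trial. The baseline characteristics in SAP 3.2.1 list no medications. Statin intensity is available as a two-level stratum, but SAP 4.2.4 holds the only visible by-class summary of antithrombotic, beta-blocker and renin-angiotensin therapy before randomization. Participants enter 30 to 365 days after an MI (Protocol 5.1), so much of this therapy will have begun in the year before first dose, and sites are asked to maximize statin intensity before randomization. Starts of this kind are the ones the two first-dose branches can reach.

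**Working it through.** The plan gives no figure on this point, so the check applies the rule to dates and then asks how often a truly earlier start is moved.

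**Step 1: can a moved record qualify?** A moved record has start date = first-dose date = Day 1. The test in SAP 4.2.4 is start date < randomization date, and the randomization date is also Day 1. The test becomes Day 1 < Day 1, which is false in every case.

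**Step 2: worked cases.** Drug ongoing, first dose 15SEP2021.

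| True start | Part missing | Imputed start | Counted as pre-randomization? |
|---|---|---|---|
| 10MAR2021 | day | 01MAR2021 | yes |
| 10MAR2021 | month | 15SEP2021 | no |
| 10NOV2020 | day | 01NOV2020 | yes |
| 10NOV2020 | month | 01JAN2020 | yes |
| 02SEP2021 | day | 15SEP2021 | no |
| 02SEP2021 | month | 15SEP2021 | no |

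Two records with the month equally unknown, one begun in March 2021 and one in November 2020, are classified oppositely because of the calendar year alone.

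**Step 3: share moved, by gap.** Let g be the days from true start to first dose, and assume that first dose is equally likely on any day of a 365-day year.

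- Month missing: the start falls in the first-dose year with probability 1 − g/365 for g up to 365, and 0 beyond. This gives 92% at g = 31, 75% at 90, 51% at 180, 26% at 270 and 0% at 365.
- Day missing: the start falls in the first-dose month with probability Σ max(L − g, 0)/365, summed over the twelve month lengths L. At g = 7 this is (365 − 84)/365 = 77%. At g = 14 it is (365 − 168)/365 = 54%. At g = 28 it is 29/365 = 8%. At g = 31 or more it is 0%.

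**Step 4: drugs begun at the qualifying MI.** Enrollment is at least 30 days after the MI and screening ends by Day −1, so g is at least 31.

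- Day missing: 0% moved.
- Month missing, g uniform on 31 to 365: mean g = 198, so 1 − 198/365 = 46%.
- Month missing, g uniform on 31 to 449: the 365-day limit applies at enrollment, and pre-screening plus screening can add 42 + 42 = 84 days. Of the 419 possible gaps, 335 are 365 or less, so (335/419) × 0.458 = 37%.

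The documents do not say how many medication records lack a month or a day, so these conditional shares cannot be turned into a number of records or subjects.

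**The case against.** The strongest reply is that little depends on this. Much of it stands.

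- **Scope.** A reader might infer that partial start dates of ongoing drugs are moved in general. They are not. A missing day outside the first-dose month goes to the first of the recorded month, and a missing month outside the first-dose year goes to 01-JAN. Both stay before randomization when the month or year is earlier.
- **Rate.** Protocol 6.5 requires start and end dates for every medication, so a missing month may be uncommon. A reader might multiply the 37% to 46% by a guessed rate of missing months and call the product the share of cardiac drugs lost. The documents support no such rate. The percentages apply only to drugs begun at the MI, and the table counts subjects, who may have another cardiac drug with a usable date.
- **Balance and efficacy.** A reader might infer that treatment comparisons are biased. The rule is the same in every arm and concerns therapy before randomization, so no differential undercount is expected. The ANCOVA and MMRM adjust for statin intensity as the stratification factor, and the strata are tabulated separately in SAP 4.2.7; none of this uses an imputed medication date.
- **Visibility.** Affected drugs remain among concomitant medications, in the listing and in the category for the end of study.
- **Redaction.** A redacted block follows the rule in SAP 3.1.1.2, so a further provision there cannot be excluded. No exception for medications is visible.

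None of this answers Step 1. In the two affected branches the misclassification is certain for any drug truly begun earlier, it runs in one direction only, and the rule brings medications no visible benefit.

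**Conclusion.** The point holds in a limited form. A medication that is ongoing or stopped on or after first dose is moved to the first-dose date in two cases: month missing in the first-dose year, or only the day missing in the first-dose month. If such a cardiac drug truly began earlier, SAP 4.2.4 cannot count it as started before randomization. The consequence is an undercount, expected to be similar across arms, in one descriptive table. Primary and secondary efficacy estimates do not change.

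The total size is unknown. The 37% to 46% for drugs begun at the qualifying MI with the month missing rests on uniform timing of first dose within the year and of the gap since the MI. With only the day missing, such drugs are not affected; drugs begun in the last 30 days before first dose are.

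Completely missing start dates, which the SAP leaves unimputed, cannot pass the test either. How to classify them is a matter of judgement and is not part of this point.

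**What to change.** In SAP 3.1.1.2, keep the current rule for adverse events and add a separate rule for medications: impute a partial start date to the earliest date consistent with the recorded part, that is, the first of the recorded month if only the day is missing, or 01-JAN of the recorded year if the month is missing. Point SAP 3.5 to the new rule. SAP 4.2.4 needs no change.

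The cost is a few lines of SAP text and one derivation; no AE output or efficacy analysis is touched. The downside is that a few drugs truly begun on study, with a partial date in the first-dose month or year, would count as pre-randomization. A footnote to the table giving the number of subjects with an imputed start date would show how much either error could matter.
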